**The Michigan Stroke Transitions Trial (MISTT): Improving Care
Transitions for Acute Stroke Patients Through a Patient-centered
Home Based Case Management Program**

NCT02653170

June 17, 2019

Analysis of Patient Outcomes

Among randomized participants, descriptive statistics of demographic and clinical data, including frequencies and contingency tables, were constructed for categorical data, while means and standard deviations were generated for continuous variables.

The original study protocol specified that the analytical model for the intention-to-treat (ITT) analysis of the primary study outcomes would involve testing the differences in the mean change over time (90-day minus 7-day values or “delta”) in each of the 3 treatment groups using a one-way ANOVA.¹ This approach is referred to as a “complete case analysis,” since for an individual participant to be included, it requires that data be available from both time points; if data are missing for either time point the participant is dropped from the analysis.

Subsequently, after completing data collection, we faced the problem of missing data at both the 7-day and 90-day time points, which negatively impacted the “complete case analysis” sample size. Specifically, only 180 patients had data available for the primary outcomes at both time points. To increase the number of observations available for the ITT analysis, we therefore modified the statistical model from the ITT “complete case analysis” to an ITT “available case analysis” which relied on the following linear regression model approach.²

The primary outcomes (PROMIS-10 GPH and GMH subscales, and PAM) were analyzed as linear (continuous) variables using Proc Mixed (SAS V9.4, Cary, NC); 7-day and 90-day outcomes were analyzed as correlated continuous responses within patient. The statistical model for the mean response comprised of an intercept, two indicators for group-2 and group-3 (group-1 as referent), one indicator for time 90-day (7-day as referent), and two group-by-time interactions. Hence the model for the mean response is:

$$\beta_0 + \beta_1 (\text{Grp2}) + \beta_2 (\text{Grp3}) + \beta_3 (90d) + \beta_4 (\text{Grp2} * 90d) + \beta_5 (\text{Grp3} * 90d).$$

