The change from 7-day to 90-day in mean response in group-1 is β_3 ; the corresponding change in group-2 is $\beta_3 + \beta_4$. Hence, the group-by-time interaction coefficient β_4 is the comparison of group-2 to group 1; β_5 is the analogous comparison of group-3 to group-1. The combined 2-degree freedom test of the group-by-time interactions (i.e., $\beta_4=\beta_5=0$) identifies whether the mean change over time differed between treatment groups. We refer to this interaction as a difference-in-differences (D-in-D) analysis or result.² Pair-wise contrasts (with 95% confidence intervals) were generated to compare treatment groups with each other.

This “available case analysis” approach has the advantage of increasing the number of individuals that contribute to the ITT analysis, since participants with data available from only one of the 2 time points can still be included. Thus, while only 180 patients (with 360 observations, one for each time point) could be included in the complete case analysis, 214 patients (with 434 observations) were included in the available case analysis. The net effect of using the available case analysis approach is that it minimized the amount of missing data and thereby reduces its potentially negative impact on the primary results. However, it does not eliminate the problem of missing data, so there is still the need to use a multiple imputation procedure which we did as part of a subsequent sensitivity analysis.

Following completion of main effects models for all the primary outcomes, we tested whether adjusting for potential confounding variables resulted in a meaningful change in the results (defined as at least a 10% change in the beta coefficient representing the effect size of each treatment group). We developed the following list of a priori potential confounders: age, race, sex, time between admission and returning home, study site, stroke severity, discharge modified Rankin score (mRS), discharge destination (home, acute rehabilitation, sub-acute rehabilitation), and consented caregiver included (yes, no). We also adjusted the analysis for any variables that were not sufficiently balanced across the 3 treatment groups following randomization. After testing for confounding effects, we determined whether each of these same variables acted as a modifier of treatment effect by testing covariate*intervention interaction terms.

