To assess the potential impact of missing data on primary patient outcomes, the analyses were repeated after missing data were generated using a multiple imputation procedure that generated 25 iterations of the fully imputed data. The linear regression results from the imputed data were then compared to the original analysis to determine if the presence of missing data had introduced any bias with respect to the statistical inferences drawn regarding overall treatment effect of the intervention (this approach can be regarded as a form of sensitivity analysis). To do this, we first applied the multiple imputation procedure 'Proc MI' (SAS software (SAS/ACCESS® 9.4) which is based on the missing at random (MAR) assumption where, using a Markov chain Monte Carlo (MCMC) method, missing outcome data are imputed using variables that are known or suspected to be associated with missing data. The Proc MI procedure imputed missing values for the primary outcomes (PROMIS-10 GPH, PROMIS-10 GMH, and PAM) each separately for the two different time points (7-day and 90-day), as well as the secondary outcomes of PHQ-9 and NeuroQOL anxiety. The imputation model included the treatment group (randomization arm) variable and the following 24 auxiliary variables: age, sex, race, stroke type (ischemic vs. hemorrhagic), past medical history/comorbidities (including history of stroke, TIA, myocardial infarction, coronary artery disease, atrial fibrillation, hypertension, hyperlipidemia, diabetes mellitus, depression, and heavy alcohol consumption), living alone prior to stroke event, having a consented caregiver, caregiver living with patient, relationship of caregiver to patient, severity of stroke (NIH Stroke Scale [NIHSS]/ Glasgow Coma Scale [GCS]), modified Rankin Scale (mRS) at discharge, score on 6-item cognitive screening test, study site, hospital discharge destination (home, acute rehabilitation, sub-acute rehabilitation), and the interval between admission and discharge to home (number of days). None of the auxiliary variables had any missing values. These auxiliary variables were chosen

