on the basis that they were statistically significantly associated with missing outcomes data, or directly described the reason for missing-ness (i.e., health-related reason, refused, or no-contact). Trace plots (across 2,500 iterations) and autocorrelation plots were used to monitor the convergence behavior of the imputation algorithm. To allow for replication of the results, a random seed number was used for all the imputations. The final imputed data set contained 13,250 observations that resulted from 25 imputations of the original 265 cases. An identical MI approach was used to impute missing values for two of the secondary patient outcomes, including PHQ-9 and Neuro-QOL anxiety.

After generating the imputed data set, the same linear regression model used in the available case analysis (generated using SAS PROC MIXED) was applied to each imputed data set. The SAS PROC MIANALYZE procedure was used to summarize these results across the 25 imputed datasets, taking into account the uncertainty in imputation due to missing data. PROC MIANALYZE generates valid statistical inferences under a missing at random (MAR) assumption by combining the estimated model coefficients and associated covariance matrices across the multiple imputed datasets. As with the available case analysis, the quantities of substantive interest were the mean responses between the two time points and among the three study arms. In the full factorial model (main effects for the treatment groups and time, and their interactions), these quantities are the combined 2-degree freedom test of the group-by-time interactions (i.e., $\beta_4=\beta_5=0$), which identifies whether the mean change over time differed between treatment groups.

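### Agreement between two analyses that both assume missing at random cannot show that missing data introduced no bias, and no analysis under missing not at random is described

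*SAP*

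**What the plan says.** **Primary analysis** (SAP, Analysis of Patient Outcomes). PROC MIXED with group, time and group-by-time terms, in which "7-day and 90-day outcomes were analyzed as correlated continuous responses within patient". The SAP moved to this model after data collection because "only 180 patients had data available for the primary outcomes at both time points". It states no missingness assumption for the model, but concedes that "it does not eliminate the problem of missing data".

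**Covariate adjustment** (same section). After the main models, "we tested whether adjusting for potential confounding variables resulted in a meaningful change in the results", using nine named covariates.

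**Missing-data sensitivity analysis** (SAP, Sensitivity Analysis to Account for Missing Data). PROC MI, "which is based on the missing at random (MAR) assumption", with 25 imputations. "The imputation model included the treatment group (randomization arm) variable and the following 24 auxiliary variables". The primary mixed model is then refitted to each imputed data set and the results are pooled, with the statement that "PROC MIANALYZE generates valid statistical inferences under a missing at random (MAR) assumption". The pooled result is set beside the primary result with a stated aim: "determine if the presence of missing data had introduced any bias with respect to the statistical inferences drawn regarding overall treatment effect of the intervention".

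No other missing-data sensitivity analysis is given for patient outcomes. Neither the SAP nor the protocol describes a delta-adjusted, tipping-point, pattern-mixture, reference-based or selection-model analysis.

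**The concern.** Both sides of the comparison are valid only under MAR. For MI and pooling the SAP says so. For the mixed model it follows from likelihood estimation on incomplete data. If missingness depends on outcome values that were never observed, both estimates move in the same direction, and their agreement says nothing about that movement.

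Such missingness is plausible here, though the SAP does not say it occurred. The outcomes are self-reported health and activation, and health-related reasons and refusal are among the reasons for missingness that the SAP names. All 24 auxiliaries are demographic, history, caregiver, hospital or discharge items, or the interval to returning home. The 7-day outcome does describe health after the return home, but only for patients who gave it.

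At stake is the robustness statement. The model was changed because of missing data, so a reader will lean on this check more than usual.

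**Working it through.** **1. The plan's own counts.** 25 imputations × 265 cases × 2 visits = 13,250, as the SAP states. Patients lacking at least one primary value: 265 − 180 = 85, and 85/265 = 32.1%.

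**2. Missing at 90 days.** The SAP gives 214 patients and 434 observations for the available-case analysis. These do not fit together: 180 × 2 + 34 = 394, not 434. Both readings are carried, with single-visit patients assumed to split evenly between visits.
- 214 patients correct: 34 single-visit, 51 with neither visit. Missing at 90 days (17 + 51)/265 = 25.7%.
- 434 observations correct: 74 single-visit, 11 with neither. Missing at 90 days (37 + 11)/265 = 18.1%.
- Any split: 11/265 = 4.2% to 85/265 = 32.1%.

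**3. What each analysis conditions on.** The primary model uses arm, visit and the observed outcome. MI adds the 24 auxiliaries. All nine covariates of the adjusted refits are among the 24, so those refits cover part of the same ground. None conditions on an unobserved outcome.

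**4. What the comparison can and cannot detect.** Large-sample simulation of the group-by-time contrast (assumed: PAM scale, SD about 13, about one third missing at 90 days, true contrast 0, value-related missingness in one arm only):

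| Missingness depends on | Bias, mixed model | Bias, MI with auxiliary |
|---|---|---|
| 7-day outcome | −0.02 | −0.02 |
| an auxiliary | −0.72 | −0.02 |
| unobserved 90-day value | −2.42 | −2.28 |
| the same, milder | −1.23 | −1.16 |

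In the second row the comparison reveals the bias. In the last two rows the analyses nearly agree and both are wrong.

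**5. Size of a possible shift.** Let f be the fraction missing at a visit and d the amount by which the missing values differ from their MAR prediction. Within an arm the mean change moves by

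f90 × d90 − f7 × d7,

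and the contrast moves by the difference of this quantity between arms.

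*Departure at 90 days only, in one active arm, d90 = 0.3 to 0.5 SD:*
- Shift: 0.181 × 0.3 = 0.054 to 0.257 × 0.5 = 0.128 SD. With the PAM SD of 13 (protocol item 20e): 0.71 to 1.67 points, below the 4.6 that item 20e calls meaningful.
- Standard error: per arm, information = n_c Σ⁻¹ + diag(n7, n90), with 60 complete patients and 34/6 = 5.7 or 74/6 = 12.3 single-visit patients per visit (equal arms assumed). With within-patient correlation 0.5 to 0.7 (assumed), the SE of a pairwise change contrast is 0.137 to 0.178 SD.
- Shift/SE: 0.31 to 0.92. Two-sided pairwise rejection under no true effect: 6.1 to 15.1%. Joint 2-df rejection, with noncentrality (4/3)(shift/SE)²: 6.0 to 14.4%.
- Over all splits of single-visit patients: shift 0.012 to 0.160 SD, pairwise rejection 5.1 to 21.3%.

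*Same departure at both visits, equal missingness:* 0.257 × 0.5 − 0.257 × 0.5 = 0, and likewise 0 at 18.1%. This holds even if only one arm is affected.

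*Equal departure and equal missingness in all arms:* 0.

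*Equal 90-day departures, 5 to 10 points more 90-day missingness in one active arm:* 0.05 × 0.3 = 0.015 to 0.10 × 0.5 = 0.05 SD; pairwise rejection 5.1 to 6.5%.

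**The case against.** - **The SAP is open about MAR.** It states the assumption twice, admits that missing data remain a problem, and calls the comparison a form of sensitivity analysis. It nowhere says that agreement proves absence of bias; the aim is read from one purpose clause. This stands, and it rules out any suggestion of concealment. But that clause is the only interpretation the SAP gives, and its scope is wider than the method supports.
- **The comparison is informative.** A reader might infer that it says nothing about bias. The documents do not support that: MI conditions on 24 variables that the primary model omits, and the second row of the table shows a bias it would reveal. A simulation in which missingness follows the auxiliaries equally in all arms, with the MNAR departure in one, gave a mean MI-minus-mixed difference of 0.00 (SD 0.03) whatever the departure. That result is largely built in by the set-up and is no evidence that the comparison is useless in general.
- **The size depends on the case chosen.** A reader might also infer that the trial's false-positive rate is 6 to 15%. It does not follow. The outcome is a change, data are missing at both visits, and non-responders who are equally unwell at both visits produce no shift. A persistent difference is at least as natural an assumption, particularly if 51 patients lack both visits. This stands in full.
- **No results are given**, so no conclusion is shown to be fragile. Also true.

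**Conclusion.** The concern holds as a limit on what may be inferred. Agreement between MI and the mixed model supports robustness under MAR, given the listed covariates and the observed outcomes. It does not show that missing data introduced no bias, and with 32% of patients lacking a primary value the gap is worth closing. Confidence in this is high, because it rests on the stated methods and not on assumed figures.

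The size is illustrative only. It runs from about zero (departures balanced across visits or arms) to 0.05 to 0.13 SD for the 90-day, single-arm case, under the assumed departure, even split, equal arms and correlation. Even the larger figure is below the meaningful PAM change: a 4.6-point shift would need a departure of about 1.4 to 2.0 SD (4.6/13 divided by 0.257 or 0.181). The practical risk is to a p-value near the threshold more than to a clinically large effect. The documents do not show that the trial's estimates are biased.

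**What to change.** 1. Reword the stated aim in the SAP's missing-data section: agreement supports robustness under MAR given the listed covariates and observed outcomes, and does not establish absence of bias.
2. Add a delta-adjusted tipping-point analysis, labelled post hoc, on the existing 25 imputed data sets. Shift the imputed values over a stated grid, for example 0 to −0.6 SD in steps of 0.1:
   - in usual care, in SWCM and in SWCM plus website, each separately; in both active arms together; and in all arms;
   - once for 90-day values only, and once for 7-day and 90-day values together.
3. Report the shift at which each primary 2-df and pairwise conclusion changes, with missingness tabulated by arm, visit and reason.

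Shifting each arm separately matters because a common shift in both active arms barely moves the contrast between them when their missingness is similar. Shifting both visits covers the case of a persistent health difference.

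Cost: one sentence and a short re-analysis, with no new data. The downside is a little more analysis and a less sweeping robustness statement.

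### As literally written, the multiple imputation fills each visit without the patient's other visit, which weakens the within-patient correlation and widens the standard errors of the change contrasts in the sensitivity analysis; the SAP must say which model was run

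*SAP*

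**What the plan says.** Under Analysis of Patient Outcomes, the SAP fits a mixed model in which "7-day and 90-day outcomes were analyzed as correlated continuous responses within patient". Its target is the two-degree-of-freedom group-by-time test, which "identifies whether the mean change over time differed between treatment groups". Only 180 patients have the primary outcomes at both visits.

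Under Sensitivity Analysis to Account for Missing Data, the aim is to learn whether missing data biased the inference on the treatment effect. The method is PROC MI with MCMC, resting on MAR. The outcomes were imputed "each separately for the two different time points (7-day and 90-day". The contents are then given: "The imputation model included the treatment group (randomization arm) variable and the following 24 auxiliary variables". The items that follow come to exactly 24 if NIHSS/GCS counts as one, and all of them are known before the 7-day interview. The SAP adds: "None of the auxiliary variables had any missing values". The same mixed model is then fitted to each completed data set and pooled with PROC MIANALYZE. Nowhere does the SAP say that the two visits were imputed together.

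**The concern.** A patient's score at one visit is likely to be the best single predictor of the score at the other. The SAP chose its auxiliaries for their link to missingness or its reasons, not for predicting the outcome, so nothing assures that they stand in for the other visit.

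If each visit is filled from arm and auxiliaries alone, the imputation model leaves out the very relation that the analysis model estimates. Two things are then at stake:

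- **Precision.** A within-patient change gains precision from the correlation between visits. Weakening it inflates the standard errors, so the sensitivity analysis leans towards finding no difference.
- **Assumptions.** Visit-by-visit imputation is valid if missingness depends only on arm and the auxiliaries. The mixed model that it is meant to check also allows missingness to depend on the observed other visit. If missingness does depend on it, differently by arm, the check can be more biased than the analysis being checked.

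**Working it through.** **The plan's own figure.** "The final imputed data set contained 13,250 observations that resulted from 25 imputations of the original 265 cases". Imputations × patients × visits = 25 × 265 × 2 = 13,250. This reproduces exactly, but fits visit-by-visit and joint imputation equally well.

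**How many patients are affected.** 265 − 180 = 85 patients (32%) lack one or both visits. The split is unclear. The SAP states that "214 patients (with 434 observations) were included in the available case analysis", but 214 patients can give at most 2 × 214 = 428 observations. That conflict needs its own correction. Both splits are carried here:

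- Trusting 434 observations: 434 − 360 = 74 patients with one visit, 265 − 180 − 74 = 11 with none, and 530 − 434 = 96 values to impute.
- Trusting 214 patients: 214 − 180 = 34 with one visit, 265 − 214 = 51 with none, and 530 − (360 + 34) = 136 values to impute.

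**Assumed inputs.** The visit correlation ρ and the share R² of outcome variance explained by the auxiliaries are not in the documents. They are varied below, with the auxiliaries acting alike at both visits.

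**Hand calculation.** Complete pairs keep correlation ρ. A pair with an imputed member has correlation of about R². So the completed-data correlation is approximately (180/265)ρ + (85/265)R² = 0.679ρ + 0.321R². The standard error of a change contrast is proportional to √(1 − correlation), taking the completed-data variance only.

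| ρ | R² | Completed-data correlation | Relative fall | Standard-error ratio |
|---|---|---|---|---|
| 0.50 | 0.40 | 0.340 + 0.128 = 0.468 | 6% | √(0.532/0.50) = 1.03 |
| 0.50 | 0.20 | 0.340 + 0.064 = 0.404 | 19% | √(0.596/0.50) = 1.09 |
| 0.65 | 0.40 | 0.442 + 0.128 = 0.570 | 12% | √(0.430/0.35) = 1.11 |
| 0.65 | 0.20 | 0.442 + 0.064 = 0.506 | 22% | √(0.494/0.35) = 1.19 |

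**Simulation.** 265 patients, three arms, 24 auxiliaries, no true effect, missingness unrelated to outcome, 10 imputations pooled by Rubin's rules, 120 to 150 replicates per row. Standard errors are for a pairwise difference in change, in SD units.

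| One visit / none | ρ | R² | Correlation, separate / joint | SE, separate / joint | Excess |
|---|---|---|---|---|---|
| 74 / 11 | 0.50 | 0.20 | 0.39 / 0.49 | 0.200 / 0.182 | 10% |
| 74 / 11 | 0.65 | 0.20 | 0.49 / 0.63 | 0.187 / 0.155 | 21% |
| 74 / 11 | 0.65 | 0.40 | 0.55 / 0.63 | 0.168 / 0.154 | 9% |
| 34 / 51 | 0.50 | 0.20 | 0.38 / 0.48 | 0.210 / 0.188 | 12% |
| 34 / 51 | 0.65 | 0.20 | 0.49 / 0.64 | 0.202 / 0.160 | 26% |

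Further runs of the same kind put the low end at about 2% (ρ = 0.5, R² = 0.40) and the high end at about 27%. At ρ = 0.8 and R² = 0.20 the excess rises to 40% (0.170 / 0.121) or 51% (0.186 / 0.123), depending on the split.

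**Bias in the change contrast** (R² = 0.20):

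- Day-90 loss depends strongly on the day-7 score, equally in every arm, true effect 0.3 SD. Separate imputation: −0.018 SD at ρ = 0.5 and +0.003 at ρ = 0.65 (Monte Carlo SE 0.011 and 0.009). Joint: −0.015 and −0.004. The bias cancels between arms.
- The dependence exists in usual care only. Separate: −0.09 SD at ρ = 0.5 and −0.14 at ρ = 0.65. Joint imputation removes it.
- The dependence runs in opposite directions in two arms, ρ = 0.65, no true effect (deliberately adverse). With the 74/11 split, separate imputation gives −0.21 SD and rejects in 18.5% of 200 runs; joint gives −0.01 SD and 5.5%. With the 34/51 split, separate gives −0.13 SD with 6.0% rejection; joint gives −0.01 SD and 6.5%.

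**The case against.** The strongest reply is that the SAP may describe one joint model. The listed items are called auxiliaries, so the variables being imputed would not be expected among them, and the other visit's absence from that list proves little. The phrase on separate time points follows three named outcomes. It could mean one run per outcome covering both visits, or two columns in a wide model. A single incomplete column with fully observed predictors is a monotone pattern that needs no MCMC, yet the SAP reports MCMC with trace and autocorrelation plots over 2,500 iterations.

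This stands as a real ambiguity but does not settle it. MCMC could also have been run at each visit on several outcomes together, and the most literal reading of the sentence remains visit by visit.

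Several stronger conclusions are tempting and are not supported:

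- A reader might infer that the within-patient correlation is destroyed. It is not: the 180 complete patients keep theirs, and the overall value is diluted.
- A reader might infer that any day-90 dropout related to the day-7 score biases the check. For the group-by-time contrast it must differ by arm, and the documents report no such pattern.
- A reader might infer that the primary result is compromised. The available-case mixed model does not use the imputed data and already treats the visits as correlated.

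It is also fair that the usual consequence is conservative, and that the size depends on two quantities the documents do not give.

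**Conclusion.** The point holds on the literal reading, with limited reach. If the visits were imputed separately, the imputation does not match the change analysis it feeds. For ρ of 0.5 to 0.65 and R² of 20% to 40%, the completed-data correlation falls by roughly 5% to 25% (for example from 0.65 to about 0.50). The standard error of a pairwise change contrast is then about 2% to 27% too wide, and more at higher correlation. Bias arises only when missingness depends on the other visit's score differently by arm, at about −0.14 SD in the usual-care-only example. The primary mixed model can handle that case under MAR; this imputation cannot. Agreement or disagreement between the two analyses would then be harder to interpret as evidence about missing-data bias.

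The fault lies in the sensitivity analysis alone. It should be corrected, but it gives no ground for setting aside the primary analysis. Confidence is moderate, because the text does not establish which imputation was run.

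**What to change.** State the full PROC MI variable list, including whether both visits were in one model and which outcomes shared a run.

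- **If the visits were imputed separately:** impute in wide format, one row per patient (265 rows), with the 7-day and 90-day values of the outcome in the same model as arm and the 24 auxiliaries. Then stack to two rows per patient, refit the planned mixed model and pool as before. Do the same for PHQ-9 and Neuro-QOL anxiety, for which the SAP used an identical approach.
- **If both visits were already in one model:** reword the sentence to say so. No rerun is needed.

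Putting all five outcomes at both visits into one model is optional. It adds information but means about 10 outcome columns beside arm and 24 auxiliaries, some with several categories, on 265 patients, so convergence would need closer checking.

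The cost is a changed variable list, a rerun and a convergence check. No new data are needed.
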